All patients enrolled in the study will have a perioperative anesthetic care plan standardized as much as possible conforming to the current institutional protocol utilized for intraoperative medication administration. Patients will be anticoagulated according to institutional practice with heparin 400 units/kg with goal ACT >400 prior to initiation of cardiopulmonary bypass. After cardiopulmonary bypass, patients will receive protamine at dose 0.01 mg/unit of heparin given with target ACT within 10% of baseline value. If ACT >10% baseline additional protamine will be given at the anesthesiologists discretion. Evaluation and determination of excessive microvascular bleeding in the surgical field will occur 10 minutes after return of ACT to within 10% of baseline. Determination for treatment with PCC or FFP will be based off of the current algorithm used at our institution.¹ Specifically this study will focus on patients with a PT >16.6 sec/ INR >1.6 sec, or aPTT > 57 sec with clinical evidence of excessive microvascular bleeding

in the surgical field as determined by the surgical team. All other coagulopathies will be treated as per the current institutional transfusion protocol.

B. Study Population

Consecutive adult patients undergoing cardiac surgery at St. Marys Hospital will be potentially eligible for the study. All of the cardiac surgeons at Mayo Clinic Rochester will be asked to participate in the study.

Inclusion Criteria

All subjects eligible for enrollment must:

1. Be ≥ 18 years of age
2. Be undergoing a cardiac surgical procedure utilizing cardiopulmonary bypass
3. Have an INR ≤ 1.3 if warfarin was not held for 5 days

Exclusion Criteria

All subjects with one of the following are not eligible for enrollment:

1. Are unable to grant informed consent or comply with study procedure
2. History of hypercoagulable condition (e.g. Factor V Leiden, AT-3 deficiency, Prothrombin gene mutation, Anti-phospholipid antibody syndrome, etc.) or previous unprovoked thromboembolic complications
3. Coagulopathic conditions such as factor deficiencies, factor inhibitors, heparin induced thrombocytopenia, or use of intravenous anticoagulants other than heparin at the time of cardiovascular surgery
4. Thromboembolic event with past 3 months
5. Received oral therapy with ELIQUIS (apixaban) or Xarelto (rivaroxaban) within 3 days prior to planned surgical procedure

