6. Received oral therapy with clopidogrel, prasugrel, or dabigatran within 5 days prior to planned surgical procedure
7. Are undergoing emergency open heart-surgery
8. Cardiopulmonary bypass time is expected to be <30 minutes
9. Are pregnant
10. Heparin allergy
11. ECMO post op
12. Life threatening bleeding necessitating transfusion of hemostatic products (FFP or PCC) prior to the study intervention time point
13. Circumstances for which the safety of the patient could be jeopardized by continued adherence to the study protocol

Enrolled subjects must meet additional criteria in order to receive study treatment:

Inclusion Criteria

1. Have evidence of excessive microvascular bleeding in the surgical field as determined by the surgical team
2. PT >16.6 sec/ INR >1.6 sec, or aPTT > 57 sec. on initial post cardiopulmonary bypass labs

Exclusion Criteria

1. Fibrinogen < 144 mg/dL on initial post cardiopulmonary bypass labs

C. Enrollment

Subjects will be enrolled at the time of pre-operative visit with cardiothoracic surgery if they meet the eligibility criteria. Informed written consent will be obtained and randomization performed to one of the two study arms.

We estimate approximately 1000 subjects will be need to consented with intent of having 100 patients receive treatment (50 patients in each treatment arm). This study will terminate once 50 patients in each study arm have received treatment. Our data and safety monitoring board (DSMB) will provide oversight and monitoring to the study to ensure the safety of participants and validity and intensity of data. The DSMB will consist of 2 physicians and a statistician not affiliated with study. They will review data from the study and meet at the 50% and 75% enrollment milestones or every 6 months from previous meeting date whichever comes first. The DSMB will provide aggregated data summaries to the Mayo IRB with explanations of seriousness and relatedness of adverse events to the study. In addition to the above, the authors will inform the National Institute of Health (NIH) of any actions taken by the IRB as a result of its continuing review.

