The primary adverse event of concern in this study would be thromboembolic events. DSMB (anesthesiologist, hematologist, and statistician) will meet quarterly, and review all data from each study arm. Thromboembolic complications will be reviewed and clinical judgment will used to determine necessity of study termination. No formal stopping rules are feasible given the study size and low incidence of TEE.

Early termination of the study will ensue if adverse events in either study arm exceed acceptable level.

D. Randomization and Blinding

Upon consent for study participation enrolled patients will be randomized via computer-generated blocks and with stratification according to the surgical procedure to either receive PCC or FFP during cardiac surgery should they develop excessive microvascular bleeding in the

surgical field as determined by the surgical team in addition to a PT >16.6 sec/ INR >1.6 sec after cardiopulmonary bypass. The randomization assignments will be concealed in opaque envelopes and disclosed to the anesthesiologist caring for the patient. The surgical and intensive care personnel will not be blinded to the treatment arm, as transparency of transfusion product is necessary to prevent overdosage of PCC and potential thrombotic complications.

E. Interventions

Patients will be consented and enrolled in the study until 50 patients have received treatment in each arm of the study. Patients will be anticoagulated according to institutional practice with heparin 400 units/kg with goal ACT >400 prior to initiation of cardiopulmonary bypass. After cardiopulmonary bypass, patients will receive protamine at dose 0.01 mg/unit of heparin given with target ACT within 10% of baseline value. After protamine administration the ACT, CBC, PT/ INR, and fibrinogen, will be collected via preexisting arterial access. If ACT >10% baseline additional protamine will be given at the anesthesiologists discretion. Evaluation and determination of excessive microvascular bleeding in the surgical field will occur 10 minutes after return of ACT to within 10% of baseline. Patients with clinical evidence of excessive microvascular bleeding in the surgical field as determined by the surgical team, along with a PT >16.6 sec/ INR >1.6 sec will receive randomized treatment with either PCC or FFP.

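### Exclusion 11 (ECMO after surgery) cannot be known at enrolment and is not limited to the time before study product, and no analysis set keeps treated patients who later meet it

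*Combined protocol and SAP*

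**What the plan says.** Section 3.B introduces thirteen exclusions with "All subjects with one of the following are not eligible for enrollment". Number 11 is "11. ECMO post op". Number 13 is "13. Circumstances for which the safety of the patient could be jeopardized by continued adherence to the study protocol". Number 12, on life-threatening bleeding, is expressly confined to the time before the study intervention; numbers 11 and 13 carry no such limit. A second, shorter list in 3.B gives the conditions for receiving study treatment. Its only exclusion is low fibrinogen, and it does not mention ECMO.

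On timing, section 3.C states "Subjects will be enrolled at the time of pre-operative visit with cardiothoracic surgery if they meet the eligibility criteria", and section 3.D states "Upon consent for study participation enrolled patients will be randomized via computer-generated blocks". Study product comes later, in theatre. Under sections 3.A and 3.E, "Evaluation and determination of excessive microvascular bleeding in the surgical field will occur 10 minutes after return of ACT to within 10% of baseline", and product follows if the bleeding and laboratory criteria are met.

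On who is counted, section 3.C says "This study will terminate once 50 patients in each study arm have received treatment". Serious adverse events are collected to 30 days (3.G item 6.c), and safety is defined as a similar rate in the two arms (3.P). Section 3.J defines no intention-to-treat, treated or safety population.

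**The concern.** Post-operative ECMO in a patient who has already received PCC or FFP is an outcome, not a baseline fact. It may follow cardiac failure or thrombosis, and it can accompany heavy bleeding. Thromboembolism is the harm that section 3.C singles out for monitoring. If such a patient is ruled ineligible afterwards and left out, the transfusion, blood-loss and serious-adverse-event comparisons are all conditioned on something that happened after treatment. Randomisation no longer protects them.

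Two features of the plan add to the exposure. Under 3.D, surgical and intensive care staff know the arm, and the blinded panel in 3.H is given outcome events to assess, not exclusions. ECMO is also absent from the serious adverse events in 3.G, so the plan mentions it only as a reason to exclude.

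**Working it through.** **Order of events.** The question is structural, so the passages are set side by side first.

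| Step | When | Source |
|---|---|---|
| Enrolment and eligibility decision | Pre-operative visit | 3.C |
| Randomisation | On consent, before surgery | 3.C, 3.D |
| Exclusion 12 can be met | In theatre, before the intervention | 3.B |
| PCC or FFP given | After bypass and protamine | 3.E |
| Exclusion 11 can be met | After surgery; no limit relative to product | 3.B |
| Exclusion 13 can be met | Any time after entry | 3.B |
| Serious adverse events counted | To day 30 | 3.G |

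Exclusion 11 cannot be evaluated at the first step, and nothing in the text stops it from being evaluated after product. Exclusion 12 shows that the list is meant to operate after randomisation, and that the authors limited timing when they wished to.

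**The plan's own power figure.** Section 3.J claims more than 85% power with 50 per group for a 0.65 SD difference by a non-parametric test. Alpha is not stated; I assume 0.05 two-sided.

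- Formula: power = Φ(0.65 × √(E × n/2) − 1.96), where E is the efficiency of the Wilcoxon test relative to the t-test.
- E = 1: 0.65 × √25 = 3.25, giving Φ(1.29) = 90.1%.
- E = 3/π = 0.955 (normal data): 0.65 × √23.87 = 3.176, giving Φ(1.216) = 88.8%. A simulated Wilcoxon test on normal data gave 88.5%.
- E = 0.864 (worst case): 0.65 × √21.6 = 3.021, giving Φ(1.061) = 85.6%.

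The stated figure reproduces. If three patients leave one arm, the E = 0.955 case becomes 0.65 × √0.955 / √(1/47 + 1/50) = 3.126, giving Φ(1.166) = 87.8%. Power falls by about one point, so the issue is bias and not lost power.

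**Illustration for safety.** The documents give no ECMO or event rates. All event counts here are assumed. The 50 treated per arm is from 3.C, 3.E, 3.J and 3.P (section 2 speaks of 100 per arm). Start from 6/50 = 12.0% with PCC and 3/50 = 6.0% with FFP.

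| Event patients removed | PCC | FFP | Difference (points) |
|---|---|---|---|
| None | 6/50 = 12.0% | 3/50 = 6.0% | 6.0 |
| 1 PCC | 5/49 = 10.2% | 6.0% | 4.2 |
| 2 PCC | 4/48 = 8.3% | 6.0% | 2.3 |
| 3 PCC | 3/47 = 6.4% | 6.0% | 0.4 |
| 1 PCC and 1 FFP | 5/49 = 10.2% | 2/49 = 4.1% | 6.1 |
| 1 FFP | 6/50 = 12.0% | 2/49 = 4.1% | 7.9 |

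The difference can shrink, stay the same or grow, depending on who is removed.

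**How often it might arise.** For an assumed rate r of post-product ECMO among 100 treated patients, the expected number is 100r and the chance of at least one is 1 − (1 − r)^100. For r = 1%, 2%, 3% and 5%, that gives 1, 2, 3 and 5 expected cases and chances of 63%, 87%, 95% and 99%.

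**The case against.** The best reply is that the heading governs enrolment. A treated patient is already enrolled, and no sentence tells anyone to withdraw that patient, stop follow-up or delete data. Exclusion 11 may have meant ECMO planned before surgery, and exclusion 13 a clause for leaving protocol treatment. Event collection to 30 days and the follow-up call make no exception for ECMO, and the 50 per arm are simply those who received treatment.

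Much of this stands: the plan permits removal by silence and does not order it. But neither benign reading is written down. Exclusion 12 shows that entries in this list can apply after enrolment, and collecting events does not settle who is analysed.

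Three stronger readings are tempting, and the documents do not support them.

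- A reader might infer that the DSMB would see a reduced event count. Section 3.C has the board review the data of both arms in full.
- A reader might infer that cases would vanish from the PCC arm only. The exclusion applies equally to both arms; loss would be differential only if the arms differ in how often ECMO follows product or in how the rule is applied.
- A reader might infer that this ECMO usually comes after product. There are no timing data. ECMO started because bypass cannot be weaned would come before product, and by the estimate in 3.C about 900 of 1000 consented patients never receive product.

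The illustration also changes no test result: Fisher's p is 0.49 for 6/50 against 3/50 and still 0.49 after one PCC removal. That is a fair limit on its weight. However, 3.P judges safety by similarity of rates and gives no margin, so the observed rates themselves carry the conclusion.

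**Conclusion.** The point holds as a should-fix. An enrolment exclusion depends on an event that can follow study product, a second presupposes a patient already in the study, and no analysis set keeps treated patients who later meet either one. Dropping them would condition the efficacy and 30-day safety comparisons on a post-treatment event, on the decision of staff who know the arm.

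This is a possibility that the text leaves open, not a removal that it requires. The size and direction of any bias cannot be computed from the documents. What can be said is that, at 50 treated per arm, each removed event lowers that arm's rate by just under 2 points in the assumed examples, and that power for the primary endpoints is hardly touched (88.8% to 87.8% with three patients lost from one arm). These figures rest on assumed event counts, two-sided alpha of 0.05 and, for power, normal data.

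**What to change.** - As an eligibility rule, limit exclusion 11 to facts known before the first randomised product is started.
- Add to 3.J: every patient who starts randomised PCC or FFP counts toward the 50 per arm, is followed to day 30, and is analysed for efficacy and safety in the assigned arm, whatever happens later.
- State that invoking exclusion 13 after product means departure from protocol treatment only, with follow-up and data retained. Its clinical use is unchanged.
- Report post-product ECMO by arm.

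The cost is protocol wording and one database field. The small downside is that a few patients with extreme blood loss or transfusion stay in the primary analyses; because those are rank-based, the influence of such values is limited.

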PCC (Kcentra) Dosage: Patients randomized to the PCC arm with evidence of microvascular bleeding and PT >16.6 sec/ INR >1.6 sec will have Kcentra 15 units/kg prepared from pharmacy.

Patients who have received **PCC** and continue to demonstrate microvascular bleeding 10 minutes after the full PCC dose has been administered will undergo repeat laboratory evaluation of PT/INR +/- CBC, and fibrinogen depending on previous lab results and product administration other than PCC. Therapy will ensue following our institutions current transfusion algorithm. Patients who received full dose PCC and continue to have microvascular bleeding in addition to a PT >16.6 sec/ INR >1.6 sec will receive FFP at a dose of 10-15 mL/kg rounded up to the nearest unit.

FFP dosage: Patients randomized to the FFP arm will continue with standard therapy per our institutional algorithm at a dose of 10-15 mL/kg rounded up to the nearest unit. Patients who have received **FFP** by randomization per the above dosage protocol and continue to demonstrate microvascular bleeding 10 minutes after product administration will undergo repeat laboratory evaluation of PT/INR +/- CBC, APTT, and fibrinogen depending on previous lab results and product administration other than FFP. Therapy will ensue following our institutions current transfusion algorithm. Patients who receive FFP per randomization and continue to have microvascular bleeding 10 minutes after product administration in addition to a PT >16.6 sec/ INR >1.6 sec, or aPTT > 57 sec will receive additional FFP.

Transfusion of coagulation products other than PCC or FFP (e.g. platelets and cryoprecipitate) will be determined by laboratory abnormalities requiring treatment within our institutions current algorithm in the presence of excessive microvascular bleeding.

Resolution of microvascular bleeding within the surgical field as determined by the surgical team is the endpoint for necessitation of transfusion, not normalization of coagulation testing.

Examples of this are as follows:

1. A patient with an INR of 1.9 and evidence of microvascular bleeding who receives either PCC or FFP, for which the microvascular bleeding resolves but the INR remains elevated at 1.7 would not receive additional transfusion.

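### The explicit rule for further FFP after the first study product names aPTT in the FFP arm only, a potential bias of unknown size in the primary unit count

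*Combined protocol and SAP*

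**What the plan says.** Section 3.E has one dosage paragraph per arm. Each covers the patient still bleeding 10 minutes after the study product.

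- **PCC arm.** The patient has "repeat laboratory evaluation of PT/INR +/- CBC, and fibrinogen depending on previous lab results and product administration other than PCC". With continued bleeding, the patient "in addition to a PT >16.6 sec/ INR >1.6 sec will receive FFP at a dose of 10-15 mL/kg".
- **FFP arm.** The patient has "repeat laboratory evaluation of PT/INR +/- CBC, APTT, and fibrinogen depending on previous lab results and product administration other than FFP". With continued bleeding, the patient "in addition to a PT >16.6 sec/ INR >1.6 sec, or aPTT > 57 sec will receive additional FFP".
- **Both arms.** Each paragraph also states: "Therapy will ensue following our institutions current transfusion algorithm".

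Other sections differ on whether aPTT belongs to the criterion at all. Section 2 defines factor-mediated coagulopathy, citing the current algorithm, by PT/INR alone. Section 3.A also cites the current algorithm but says: "Specifically this study will focus on patients with a PT >16.6 sec/ INR >1.6 sec, or aPTT > 57 sec". Section 3.B lets an enrolled patient receive study treatment on PT/INR or on aPTT. Section 3.D and the opening of 3.E return to PT/INR alone, and the post-protamine tests listed in 3.E do not include aPTT.

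Section 3.J makes units of allogenic product a primary endpoint, together with 24-hour blood loss. Section 3.P counts a significant reduction in either one as efficacy.

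**The concern.** Consider two patients with the same continued bleeding, PT/INR at or below threshold, and aPTT above 57 sec. On the explicit sentences of 3.E, the one assigned to FFP receives more FFP. The one assigned to PCC has no stated FFP rule for that result, and the repeat panel may not show the result at all.

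The extra units would then come from the arm-specific instruction, not from the effect of the first product, yet they count in a primary endpoint. Because 3.P accepts either endpoint, a shift in units alone could support an efficacy claim. The treating staff know the assignment (3.D), so nothing prevents an arm-specific rule from being applied as written.

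**Working it through.** **1. The plan's own figure.** 3.J states power above 85% for a 0.65 SD difference in chest tube drainage with 50 per group and a non-parametric test. Alpha is not stated; I assume 0.05 two-sided. Power = Φ(0.65 × √(50 × ARE / 2) − 1.96), where ARE is the efficiency of the Wilcoxon test relative to the t-test.
- ARE 1: 90.2%
- ARE 3/π: 88.8%
- ARE 0.864 (lower bound): 85.6%

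The claim reproduces. It concerns blood loss and does not depend on this point. The plan gives no figure for re-dosing.

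**2. The two rules side by side (3.E).**

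| | PCC arm | FFP arm |
|---|---|---|
| Repeat tests | PT/INR, with or without CBC and fibrinogen | PT/INR, with or without CBC, APTT and fibrinogen |
| Trigger for further FFP | PT/INR | PT/INR or aPTT > 57 sec |
| Reference to institutional algorithm | yes | yes |

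The panel and the trigger differ in the same direction.

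**3. Who is affected.** Only patients who are still bleeding, have PT/INR at or below threshold, and have aPTT above 57 sec. Section 3.B makes such patients foreseeable, because aPTT alone can qualify a patient for treatment in either arm. The documents give no frequency.

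**4. Illustrative shift in units.** Assumptions: an 80 kg patient, 250 mL per unit, a full further course of 10-15 mL/kg, and no FFP for the matching PCC patients.
- Volume: 80 × 10 = 800 mL; 80 × 15 = 1200 mL.
- Units, rounded up: 800/250 → 4; 1200/250 → 5. Over 70-90 kg and 200-300 mL per unit, the range is 3 to 7.
- Shift in the FFP-arm mean = q × units, where q is the share re-dosed on aPTT alone:
  - q = 5%: 0.05 × 4 to 5 = 0.20 to 0.25
  - q = 10%: 0.40 to 0.50
  - q = 20%: 0.80 to 1.00

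**5. Effect on a rank test.** A mean shift does not show what happens to a non-parametric test, so I simulated a two-sided Wilcoxon test at 5%: 50 per arm, 4000 runs per setting, no true difference, and negative binomial counts (mean 4 or 8, dispersion 1). A share q of the FFP arm received 2 or 4 extra units. All of these inputs are assumptions.

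| q | Rejection rate |
|---|---|
| 0 | 4.6-5.3% |
| 5% | 4.7-5.1% |
| 10% | 5.4-7.8% |
| 20% | 6.3-19.0% |
| 30% | 8.9-33.7% |

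The excess rejections favour PCC. If such re-dosing is rare, the effect on the test is negligible; if it is common, it is not. With one rule for both arms, this arm-specific shift is removed by construction.

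**The case against.** The strongest objection is that both paragraphs send further therapy to the institutional algorithm, and 3.A links that algorithm to PT/INR or aPTT. Nothing forbids FFP for a PCC patient with an isolated raised aPTT, and the algorithm figures, which might settle the matter, are not shown. This stands: a reader might infer that an aPTT trigger exists only in the FFP arm and that the unit count is biased by rule, but the documents do not establish either. The reference does not remove the inconsistency, however. If the algorithm includes aPTT for both arms, the explicit PCC sentence and panel omit it; if it does not, the FFP sentence adds it. Section 2 and 3.A also describe the same algorithm differently.

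Several further points stand in whole or in part:

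- APTT is an optional test even in the FFP arm, and 3.G lists it among the intraoperative variables recorded, without distinction by arm. The difference in panels is therefore softer than it first looks.
- aPTT comes and goes across Sections 2 and 3.A to 3.E, so this may be uneven drafting and not an intended asymmetry. The repair is the same.
- A reader might infer that the amount of further FFP also differs, since only the PCC sentence states it. That is weak: the FFP paragraph opens with 10-15 mL/kg and refers back to that dosing.
- A reader might infer that PCC patients would lose more blood in 24 hours. The text does not fix that direction. The algorithm remains open to them, and 3.E leaves bleeding that persists despite normal tests to clinical discretion.

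**Conclusion.** The explicit sentences of 3.E differ by arm in both the repeat panel and the trigger for further FFP, and the difference bears on a primary endpoint. Followed literally, the direct effect can only be to add FFP units to the FFP arm, which favours PCC.

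This is a potential bias of unknown size. It depends on how often bleeding continues with an isolated raised aPTT, and on whether the algorithm already brings aPTT back for PCC patients; the documents answer neither. The shift of 0.2 to 1.0 units per patient is illustrative and rests on assumed frequencies of 5% to 20%, an assumed body weight and unit volume, and no matching FFP in the PCC arm. The direction for 24-hour blood loss is undetermined, and the stated power is unaffected. The inconsistency in the text is certain; the bias is not.

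**What to change.** Reconcile the two dosage paragraphs of 3.E with each other, with Sections 2, 3.A, 3.B and 3.D and the opening of 3.E, and with the study algorithm. The repeat laboratory panel and the trigger for further FFP should be worded identically in both arms. The choice of threshold and amount belongs to the investigators.

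Report, by arm, the number of patients given further FFP after the first study product and the trigger each one met. Include any patients already treated under the current wording, so that a reader can see how many were re-dosed on aPTT alone.

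The cost is a wording amendment and possibly one added aPTT on a sample already drawn in the PCC arm.

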6. Postoperative variables:
- a. Allogenic blood product transfusion
 - b. Mediastinal and chest tube output for 24 hours after chest closure
 - c. **Serious Adverse Events** occurring within 30 days of operation:
 - i. Thromboembolic events (new DVT or arterial thrombosis diagnosed by Doppler ultrasound, cerebrovascular accident or transient ischemic attack, new myocardial infarction, end organ ischemia secondary to thromboembolic phenomenon, all-cause mortality)
 - 1. The concern for thromboembolic complications is certainly present, and will be monitored closely as an adverse event in both treatment arms. The presence of clinically significant thromboembolic complications will be diagnosed as per current clinical practice in this patient population. It is assumed that clinical symptomatology or suspicion to such diagnoses will trigger diagnostic testing when deemed appropriate, and any confirmed diagnoses of thromboembolic complications will be noted. No specific screening tests will occur in patients enrolled for this study.
 - ii. Renal failure necessitating unplanned initiation of dialysis or hemofiltration
 - iii. Acute Respiratory Distress Syndrome (ARDS) by Berlin definition¹⁷
 - iv. Direct transfusion related complications/reactions
 - 1. TRALI (Transfusion related acute lung injury) by standard definition¹⁶
 - 2. ABO/Non-ABO hemolytic reaction
 - 3. Anaphylactic or Allergic reaction
 - d. Length of stay (ICU and total hospital stay)

H. Outcomes

All suspected outcome events will be evaluated in a standardized way by an adjudication panel that will be unaware of the patients' assignments.

In the study, outcome measures for efficacy will be total allogenic blood products transfused and 24 hour postoperative blood loss. Outcome measure for safety will be rate of serious adverse events.

Length of stay in the ICU and hospital will also be recorded in both groups.

I. Follow-Up

A telephonic assessment will be made by a study nurse at 30 days + 7 days. A standardized phone survey will be used to obtain information for assessing events of interest (Attached below).

J. Statistics/Power Analysis

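### The thromboembolic category counts every 30-day death, does not name pulmonary embolism, and leaves unclear whether clots found other than by Doppler are counted

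*Combined protocol and SAP*

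**What the plan says.** Section 3.C (Enrollment), in its text on the DSMB, singles this category out: "The primary adverse event of concern in this study would be thromboembolic events". Section 3.G (Data Collection), item 6.c, lists the serious adverse events "occurring within 30 days of operation". There are four: thromboembolic events (i), renal failure needing dialysis or hemofiltration (ii), ARDS (iii) and transfusion reactions (iv).

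Item i is defined by a bracket. It opens "Thromboembolic events (new DVT or arterial thrombosis diagnosed by Doppler ultrasound, cerebrovascular accident or transient ischemic attack, new myocardial infarction" and closes "end organ ischemia secondary to thromboembolic phenomenon, all-cause mortality". Death has no line of its own in items i to iv.

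The sub-item directly under the bracket takes a broader view. It says "The presence of clinically significant thromboembolic complications will be diagnosed as per current clinical practice in this patient population", adds that "any confirmed diagnoses of thromboembolic complications will be noted", and states that "No specific screening tests will occur in patients enrolled for this study".

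Section 3.H (Outcomes) makes the overall serious adverse event rate the safety outcome and sends suspected outcome events to a panel unaware of assignment. Section 3.J calls that rate exploratory. Section 3.P judges safety by whether the rate is similar in the two arms.

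**The concern.** The category has two faults, which pull in different directions.

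- **It includes too much.** A death from bleeding, sepsis or pump failure meets the definition of a thromboembolic event. Such deaths add events unrelated to clotting and pull the ratio between arms towards 1. If the products also differed in their effect on bleeding deaths, the two effects would be mixed in one count.
- **It may include too little.** Pulmonary embolism is not named, and the wording "new DVT or arterial thrombosis diagnosed by Doppler ultrasound" does not cover a clot shown by CT, by angiography, at surgery or at autopsy. The sub-item has such a diagnosis noted but does not say that it is counted. Two adjudicators could classify the same CT-proven embolism differently.

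At stake is whether the thromboembolic figure means what its label says. Section 3.C provides for no formal stopping rule and relies on clinical judgment about these events. An embolism that is noted but not counted could also drop out of the listed serious adverse event rate on which Section 3.P judges safety.

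**Working it through.** **1. What the text includes.** Reading the bracket and the sub-item side by side:

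| Event within 30 days | Bracket in 6.c.i | Sub-item below it |
|---|---|---|
| Death from a non-thrombotic cause | Counted | Not addressed |
| Stroke or TIA, MI, end-organ thromboembolic ischemia | Counted, no imaging limit | Noted |
| DVT or arterial thrombosis seen on Doppler | Counted | Noted |
| DVT or arterial thrombosis found by another method | Not covered as worded | Noted; counting not stated |
| Pulmonary embolism | Not named | Noted; counting not stated |

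The Doppler phrase could be read as qualifying arterial thrombosis only. That would free DVT from the limit but leave the other gaps.

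**2. The plan's own figure.** The only power figure is in Section 3.J: more than 85% at 50 per group for a 0.65 SD difference in blood loss with a non-parametric test. Assuming two-sided alpha of 0.05, which is not stated, a normal approximation gives 90.1%. Scaling n by the Wilcoxon efficiency of 0.955 gives 88.8%, and by the worst-case 0.864 gives 85.6%. The figure reproduces, but it concerns efficacy. The plan gives no thromboembolic or death rate and no power for either.

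**3. Illustration of the dilution.** Every rate here is an assumption. The size is 50 treated per arm, as in Sections 3.C, 3.E, 3.J and 3.P (Section 2 says 100). Power is the exact power of Fisher's test, two-sided 0.05. Section 3.J names that test for categorical variables in its paragraph on baseline comparisons; none is named for adverse events.

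With thromboembolism at rate T and unrelated death at rate d, independent of each other:

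rate counted = 1 − (1 − T)(1 − d)

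For T = 5% (FFP) and 15% (PCC), with d = 4% in both arms:

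- FFP: 1 − 0.95 × 0.96 = 0.088
- PCC: 1 − 0.85 × 0.96 = 0.184
- Ratio: 0.15/0.05 = 3.0 becomes 0.184/0.088 = 2.1
- Absolute difference: 10.0 points becomes 9.6 points
- Fisher power: 24.4% becomes 18.8%

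**4. Range.** For T = 4% against 12% (true ratio 3.0):

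| Unrelated deaths per arm | Rates counted | Ratio | Fisher power |
|---|---|---|---|
| 0% | 4.0% and 12.0% | 3.00 | 17% |
| 2% | 5.9% and 13.8% | 2.32 | 14% |
| 4% | 7.8% and 15.5% | 1.98 | 13% |
| 6% | 9.8% and 17.3% | 1.77 | 12% |

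If, in the 4% row, 25% or 50% of thromboembolic events also went uncounted, the ratio would be 1.84 or 1.65 and power 8% or 4%. The uncounted share cannot be derived from the documents.

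**5. Sample size.** With a clean definition, power is only 24% for 5% against 15% and 17% for 4% against 12%. The definition lowers a power that is already low.

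**The case against.** The strongest reply is that little depends on this bracket. The formal safety outcome is the overall serious adverse event rate, one level above it, and a death belongs in that rate wherever it is listed. The DSMB is to review all data from each arm, and its physicians can tell a bleeding death from a stroke. The sub-item records any confirmed thromboembolic diagnosis, and the telephone script asks about blood clots in general, so an embolism would probably come to light. This all stands. It limits the point to the content of one category. It does not settle whether a noted event is counted, and it does not take non-thrombotic deaths out of the thromboembolic count.

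A reader might infer three stronger things that the documents do not support:

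- **That the main safety outcome is masked.** Thromboembolism is the event of most concern, but the stated outcome is the overall rate.
- **That every pulmonary embolism is lost.** The sub-item has it recorded; only its counting is unclear. Nor do the documents say that the panel applies the bracket literally.
- **That opposite effects will cancel and hide an excess.** Such a case can be constructed. Thromboembolism of 5% against 10%, with other deaths of 6% on FFP and 2% on PCC, gives 1 − 0.95 × 0.94 = 10.7% against 1 − 0.90 × 0.98 = 11.8%, a ratio of 1.1. But it assumes a threefold difference in other deaths that nothing in the documents supports, and no passage says that the bracket is analyzed as a single number. Even with a clean definition, power for 5% against 10% is about 6%, so the rewording would not make that doubling detectable by a test.

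**Conclusion.** The point holds as a fault in how one category is defined. Three facts rest on the text alone: all-cause death sits inside the thromboembolic bracket, pulmonary embolism is not named, and the Doppler wording disagrees with the sub-item beneath it.

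The consequence is conditional. If the bracket is applied as written, the thromboembolic count includes non-thrombotic deaths. A pulmonary embolism or a CT-detected clot may be recorded yet left out of that count and of the listed serious adverse event rate. Under the assumed rates the dilution is moderate: the ratio falls from 3.0 to about 1.8 to 2.3 with 2% to 6% unrelated deaths, while the absolute difference barely moves. This does not show that the safety outcome is masked, and the small sample is the larger reason an excess could be missed. The definition still merits correction, because judgment will rest on few events: 2.5 expected against 7.5 at 5% and 15% of 50. One or two misclassified cases could change the reading.

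**What to change.** In Section 3.G, item 6.c:

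1. List all-cause mortality as its own serious adverse event line.
2. Count a death as thromboembolic only when the blinded panel adjudicates it so.
3. Name pulmonary embolism in the thromboembolic definition.
4. Accept DVT, pulmonary embolism and arterial thrombosis confirmed by any imaging, at surgery or at autopsy. State that events noted under the sub-item are counted, so that bracket and sub-item agree.
5. Report each component by arm, with a confidence interval.

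The cost is wording in Section 3.G and on the adjudication form. Removing unrelated deaths makes the thromboembolic count slightly smaller; the overall serious adverse event rate still includes them. No new tests are needed, since detection stays symptom-driven as the plan has it.
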